8.2 Data collection

Designated Investigator staff will enter the data required by the protocol into the eCRFs using fully validated software that conforms to 21 CFR Part 11 requirements. Designated Investigator site staff will not be given access to the EDC system until they have been trained. Automatic validation programs check for data discrepancies and, by generating appropriate error messages, allow the data to be confirmed or corrected before transfer of the data to Novartis or the CRO working on behalf of Novartis. The Investigator must certify that the data entered into the eCRFs are complete and accurate. After database lock, the Investigator will receive a CD-ROM or paper copies of the subject data for archiving at the investigational site.

All data captured for this study will have an external originating source (either written or electronic); the eCRF is not considered as source.

8.3 Database management and quality control

All data should be recorded, handled and stored in a way that allows its accurate reporting, interpretation and verification.

Novartis staff or the CRO working on behalf of Novartis will review the data entered into the eCRFs by investigational staff for completeness and accuracy and instruct the site personnel to make any required corrections or additions. Queries are sent to the investigational site using an electronic data query. Designated Investigator site staff is required to respond to the query and confirm or correct the data. If the electronic query system is not used, a paper Data Query Form will be sent (e.g., fax, e-mail) to the site. Site personnel will complete and sign the copy, then send it (with original signature) back to Novartis staff or CRO working on behalf of Novartis, who will make the correction to the database.

Concomitant medications entered into the database will be coded using the WHO Drug Reference List, which employs the Anatomical Therapeutic Chemical classification system. Medical history/current medical conditions and AEs will be coded using the Medical Dictionary for Regulatory Activities (MedDRA) terminology.

Certain laboratory samples will be processed centrally and the results will be sent electronically to Novartis (or a designated CRO).

Randomization codes in Part 2 will be tracked using an Interactive Response Technology (IRT). An internal Novartis IRT (NIRT) system will be used in Part 2. The data will be sent electronically to Novartis (or a designated CRO).

The occurrence of any protocol deviations will be determined. After these actions have been completed and the database has been declared to be complete and accurate, it will be locked and the treatment codes will be unblinded and made available for data analysis. Any changes to the database after that time can only be made by joint written agreement between the Global Head of Clinical Information Sciences and the Clinical Franchise Head.

Corporate Confidential Information

8.4 Data Monitoring Committee

A DMC will be constituted. The mission of the DMC will be to ensure the ethical conduct of the study and to protect the safety interests of patients in this study. The DMC will be responsible for reviewing the safety and efficacy results from the interim and final analyses, as well as overseeing the data accruing in the trial at regular intervals. It is expected that the DMC may consist of a nephrologist, transplant surgeon, statistician, and infectious disease specialist.

Details on the working procedures of the DMC are described in the DMC Charter.

8.5 Adjudication Committee

Not required for Part 1.

Since the study is open-label for investigators, for Part 2 an independent and blinded Adjudication Committee (AC) has been appointed in order to centrally evaluate all events reported as acute rejection, delayed graft function or other kidney dysfunction in an unbiased manner.

Details on the working procedures of the AC are described in a separate AC charter. An additional supportive PD analysis will be performed for BPAR and tBPAR based on adjudicated results.

9 Data analysis

Data from Part 1 and Part 2 will be presented separately.

9.1 Analysis sets

Part 1 and Part 2:

The Full Analysis Set will include all subjects that received at least one dose of study drug and who were transplanted.

The Safety Analysis Set will include all subjects that received at least one dose of study drug.

The PK Analysis Set will include all subjects with at least one available valid (i.e., not flagged for exclusion) PK concentration measurement, who received any study drug and experienced no protocol deviations with relevant impact on PK data.

The PD Analysis Set will include all subjects in the Full Analysis set with available PD data and no protocol deviations with relevant impact on PD data.

For all analysis sets, subjects will be analyzed according to the study treatment(s) received.

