Investigational drug	The study drug whose properties are being tested in the study; this definition is consistent with US CFR 21 Section 312.3 and is synonymous with “investigational new drug” or “investigational medicinal product”.
Investigational treatment	All investigational drug(s) whose properties are being tested in the study as well as their associated treatment controls.
	This includes any placebos, any active controls, as well as approved drugs used outside of their indication/approved dosage or tested in a fixed combination.
	Investigational treatment generally does not include other treatments administered as concomitant background therapy required or allowed by the protocol when used within approved indication/dosage.
Medication number	A unique identifier on the label of each study drug package in studies that dispense study drug using an IRT system.
Subject number	A number assigned to each subject who enrolls in the study. When combined with the center number, a unique identifier is created for each subject in the study.
Period	A minor subdivision of the study timeline; divides phases into smaller functional segments such as screening, baseline, titration, washout, etc.
Premature subject withdrawal	Point/time when the subject exits from the study prior to the planned completion of all study assessments.
Randomization number	A unique identifier assigned to each randomized subject, corresponding to a specific treatment arm assignment.
Stage	A major subdivision of the study timeline; begins and ends with major study milestones such as enrollment, randomization, completion of treatment, etc.
Study completion	Point/time at which the subject came in for a final evaluation

visit.

Study drug/treatment	Any drug (or combination of drugs) administered to the subject as part of the required study procedures; includes investigational drug, active drug run-ins or background therapy: CFZ533 + tacrolimus and CFZ533 + mycophenolate mofetil
Study drug discontinuation	Point/time when subject permanently stops taking study drug (any component of the regimen) for any reason.
Subject	An individual who has consented to participate in this study. The term Subject may be used to describe either a healthy volunteer or a patient.
Variable	Information used in the data analysis; derived directly or indirectly from data collected using specified assessments at specified time-points.

Corporate Confidential Information

Corporate Confidential Information

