3.1.2 All cohorts

Before any study-related evaluations are performed, the patient must give written informed consent. Once consent is obtained, pre-transplant screening and baseline assessments will occur to determine the patient's eligibility to participate in the study starting up to 28 days prior to transplantation. If the screening, baseline and study Day 1 visits occur in close proximity of each other (i.e., within a 12 hour timespan), certain repeated assessments may be omitted, as noted in the [Assessment schedule](#). Data collection from assessments performed at the clinical site as part of medical standard of care but prior ICF sign-off is acceptable in order to confirm patient eligibility for patients receiving an organ from a deceased donor, if assessed shortly before transplantation (i.e within 24h – matching the baseline window of Day -1 to Day 1) and in-line with inclusion and exclusion criteria.

Day 1 is defined as the day of randomization/enrollment and transplantation. This protocol defines 7 days to a week and 4 weeks (or 28 days) to a Study Month. For example, Week 2 is considered to start on Day 8 and Study Month 2 is considered to start on Week 5/Day 29. Randomization/enrollment should occur within 24 hours pre-transplant and drug administration will begin after randomization/enrollment. If CFZ533 is to be administered, the first dose of CFZ533 will be administered IV pre-transplant or intra-operatively, and must be completed by the time of unclamping. Other study drugs must be started within 24 hours post-transplant or according to local practice.

Patients who are randomized/enrolled but not transplanted will be replaced. All randomized/enrolled subjects are expected to continue in the study up to Month 6 (Part 1) or Month 12 (Part 2) regardless of being on or off randomized/assigned treatment. All subjects will be followed-up for safety (e.g., SAEs) for approximately three months after their last dose of CFZ533 or 2 months after the EoS visit for patients on SoC treatment.

[figure not shown]
Any treatment arm in which the rejection rate fulfills the *a priori* defined stopping rules (see [Section 5.5.10](#)) will be immediately discontinued at any time during the study.

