3.1.4 Part 2 – Arms 2A-2B

Figure 3-3 Part 2 Design

Approximately 45 patients who meet the inclusion criteria will be randomized in a 2:1 fashion within 24 hours pre-transplant to receive one of the 2 treatment arms (Figure 3-3):

1. **Arm 2A**, n=30: Basiliximab 20 mg (Days 1, 4) + **CFZ533 at 10 mg/kg IV** (17 doses) + MMF 1.0g BID + CS
2. **Arm 2B Control/SoC**, n=15: Basiliximab 20 mg (Days 1, 4) + Tac (4-11 ng/mL) + MMF 1.0 g BID + CS

Induction therapy must be started within 2 hours prior to transplantation, or according to local practice.

The first dose of CFZ533 will be administered IV pre-transplant or intra-operatively. Drug administration will begin after randomization and must be completed by the time of unclamping. Subsequent doses of CFZ533 will be administered IV (Arm 2A), over a period of 12 months.

Other study drugs (apart from Basiliximab) should be started within 24 hours post-transplant. The second dose of basiliximab will be administered on Day 4, or according to local practice.

The day of randomization and transplant will be considered to be study Day 1. Further treatment will be given on study Days 3, 7, 15, 29, 43, 57 and then monthly thereafter until Months 12 (up to approximately Day 337). Subjects will then undergo Study Completion evaluations.

The primary endpoint of Part 2 will be assessed to determine whether the success criteria (safety and tBPAR) have been met

Corporate Confidential Information

Corporate Confidential Information

If notable AEs or safety concerns meeting the *a priori*-defined stopping criteria (see [Section 5.5.10](#)) one of the planned dose levels may be changed or discontinued via amendment.

Subjects will undergo Study Completion evaluations at the end of the trial.

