5.4 Treatment blinding

This is an open-label, exploratory study and it is not planned to blind patients or site staff to treatment. In Part 1 since there is just one treatment arm, it will be known to the whole Clinical Trial Team that the subjects all received 3mg/kg CFZ533. In Part 2, core Clinical Trial Team members will be unblinded to continuously review safety and clinical data and evaluate the stopping rules.

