These calculations assume that the primary efficacy variable, rate of tBPAR, follows a binomial distribution. The prior distribution for the control tBPAR rate, Beta(1, 13), is estimated from a Bayesian meta-analysis of tBPAR rates from four previous studies using a control treatment similar to the one used in this study. The four studies were selected from the studies used in a previous Novartis generated meta-analysis studies and are summarized in Table 9-1.

Table 9-1 Summary of historical control data

Study	Treatment	Number of patients with tBPAR	Total number of patients	tBPAR rate
1 - Vincenti et al 2007	B+Tac+MMF+CS	24	346	0.069
2 - Silva et al 2007	B+Tac XL+MMF+CS	17	214	0.079
3 - Silva et al 2007	B+Tac+MMF+CS	8	212	0.038
4 - Scholten et al 2006	B+Tac+ MMF(0.5g)+CS	4	63	0.063

B=basiliximab

Prediction of the control rate for a future trial resulting from the Bayesian meta-analysis is shown in Figure 9-3.

Figure 9-3 Results of Bayesian meta-analysis prediction

[figure not shown]

Figure 9-3 shows estimates of response rate and 95% credible intervals for each study based on study data alone (dashed lines) and from the meta-analysis (solid lines). The overall prediction for response rate in a future study is shown in red together with the mean and 95% credible interval from the posterior distributions and n^* , the prior number of observations that these data would contribute to a future analysis.

To allow for a simple randomization ratio for allocation of patients to treatment groups, it was decided to reduce the control arm to 15 patients, compared to 30 for the CFZ533 arms. Thus a prior beta distribution of Beta (1, 13) was chosen, which has a mean value of 7 with 95% CI (0.2, 24) and an approximate weight of 14 patients.

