1.4.3 Study “stopping” rules

The following stopping rules based on potential toxicities will serve as the basis for placing the study on hold. Although the stopping criteria do not incorporate an absolute requirement for causality, the potential relationship between an AE and CFZ533 will be evaluated carefully on a case-by-case basis between the Sponsor and the Investigator. Following a review of the AE(s), a decision to permanently discontinue enrollment or re-initiate CFZ533 dosing will be made by the DMC.

- Two (2) or more patients presenting with post-transplant lymphoproliferative disease or progressive multifocal leukoencephalopathy in the CFZ533 treatment arm.

In addition, specific stopping rules for the incidence of tBPAR will be applied. These rules are designed to ensure that an arm will be stopped if there is high probability ($> 90\%$) that the true tBPAR rate is greater than 20%. Based on this stopping rule, the maximum number of patients with tBPAR for various different illustrative sample sizes would be as follows:

Table 1-1 Study stopping rules for tBPAR

Total number of patients (N)	Number of patients with tBPAR that would lead to stopping the treatment arm (n)	Observed tBPAR rate (n/N)
3	2	0.67
4	2	0.50
5	3	0.60
6	3	0.50
7	3	0.43
8	4	0.50
9	4	0.44
10	4	0.40
11	5	0.45
12	5	0.42
13	5	0.38
14	5	0.36
15	6	0.40
16	6	0.38
17	6	0.35
18	6	0.33
19	7	0.37
20	7	0.35
21	7	0.33
22	7	0.32
23	8	0.35
24	8	0.33
25	8	0.32
26	8	0.319
27	9	0.33
28	9	0.32
29	9	0.31
30	9	0.30

In addition to the automatic hold criteria and tBPAR criteria presented above, the DMC will review safety data regularly as outlined in their charter during quarterly and ad hoc meetings. The DMC can recommend stopping a specific study arm(s) or the entire trial if significant changes or effects that, in their collective opinion, are deemed unsafe or unethical to continue administering CFZ533.

2 First interpretable results (FIR)

First interpretable results (FIR) will be provided for this trial.
Corporate Confidential Information

Corporate Confidential Information

4 Statistical methods: Analysis sets

For patients for which the actual treatment received does not match the randomized treatment, the treatment actually received will be used for the analysis.

The Full Analysis Set will include all patients that received at least one dose of study drug and who were transplanted.

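### tBPAR is analysed only by treatment received: this open-label randomised PoC comparison has no specified analysis by randomised arm

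*Protocol*

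**What the plan says.** Protocol Section 9.1 sets two conditions for the FAS: "The Full Analysis Set will include all subjects that received at least one dose of study drug and who were transplanted". It then adds a rule for every set: "For all analysis sets, subjects will be analyzed according to the study treatment(s) received". SAP Section 4 agrees. Where actual and randomised treatment differ, "the treatment actually received will be used for the analysis". The SAP's modified FAS narrows the FAS by donor and graft characteristics and does not restore the randomised arm.

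The visible text does not name the set for the primary tBPAR analysis. The FAS is named for baseline summaries, eGFR and NODAT. The SAP treats tBPAR under its pharmacodynamic section, and the PD set is a subset of the FAS. Every one of these sets is analysed by treatment received, so the point holds whichever is used.

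On design, Protocol Section 3.1.4 says: "Approximately 45 patients who meet the inclusion criteria will be randomized in a 2:1 fashion within 24 hours pre-transplant". Section 5.4 says that "it is not planned to blind patients or site staff to treatment". Section 3.1.2 adds: "Patients who are randomized/enrolled but not transplanted will be replaced". The glossary entry for study drug reads, in part, "includes investigational drug, active drug run-ins or background therapy: CFZ533 + tacrolimus and CFZ533 + mycophenolate mofetil".

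**The concern.** Randomisation makes the two arms comparable as assigned. Once a patient is counted under the drug actually given, the comparison also depends on why that drug was given. Part 2 is open-label and randomisation precedes surgery, so a choice of initial treatment could reflect knowledge of both the assignment and the patient's risk. Protocol Section 3.2 itself accepts that investigator bias can affect patient management in an open-label setting. The blinded adjudication committee addresses how rejection events are read. It does not address which arm a patient is counted in.

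At stake is the primary PoC decision, which rests on a small number of events in about 45 patients. If even one patient starts on the other arm's drug, the plan gives the reader no randomised comparison with which to check the result.

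**Working it through.** **Inputs.** The arm sizes are 30 and 15 (Protocol Section 9.6: "it was decided to reduce the control arm to 15 patients, compared to 30 for the CFZ533 arms"). The priors are Beta(1/3, 1/3) for CFZ533 and Beta(1, 13) for control, and PoC is declared if Pr(θ_CFZ533 − θ_SoC < 0.20 | data) exceeds 60% (Protocol Section 9.4.2, SAP Section 6.1.3). The true rates used in step 4 are assumptions.

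**Formula.** With r tBPAR in n CFZ533 patients and s in m control patients, the posteriors are Beta(1/3 + r, 1/3 + n − r) and Beta(1 + s, 13 + m − s). The PoC probability is the integral over y of f_SoC(y) × F_CFZ533(y + 0.20), where f is the density and F the distribution function. It was evaluated numerically.

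**Step 1: reproduce the plan's figures.** At 30 v 15, the last pass and first fail are:

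| Control tBPAR | Last pass | First fail |
|---|---|---|
| 0 | 6 events, 0.656 | 7 events, 0.495 |
| 1 | 7 events, 0.642 | 8 events, 0.496 |
| 2 | 8 events, 0.633 | 9 events, 0.498 |

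The failing counts of 7, 8 and 9 match Protocol Appendix 3. Summing over Binomial(30) × Binomial(15) with a control rate of 10%, the chance of meeting the PoC rule is 79.4% at a CFZ533 rate of 20% and 82.9% at 19%. At 35% v 10% the chance of not meeting it is 80.9%. These agree with Protocol Section 9.6, which states more than 80% below a 20% rate and about 80% respectively.

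**Step 2: relabel one CFZ533-randomised patient as control.**

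| Diverted patient | As randomised | As treated | Decision |
|---|---|---|---|
| Rejects | 7/30 v 0/15: 0.495 | 6/29 v 1/16: 0.740 | fail to pass |
| Rejects | 8/30 v 1/15: 0.496 | 7/29 v 2/16: 0.717 | fail to pass |
| Does not reject | 7/30 v 1/15: 0.642 | 7/29 v 1/16: 0.597 | pass to fail |
| Does not reject | 8/30 v 2/15: 0.633 | 8/29 v 2/16: 0.583 | pass to fail |

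For the first row, the as-randomised posteriors are Beta(7.333, 23.333) and Beta(1, 28). As treated they are Beta(6.333, 23.333) and Beta(2, 28). The observed difference falls from 23.3 points to 20.7 − 6.3 = 14.4 points. In the third row it rises from 23.3 − 6.7 = 16.7 points to 24.1 − 6.3 = 17.9 points (differences taken before rounding).

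In the reverse crossover, counting a rejecting control patient as CFZ533 turns 7/30 v 1/15 (0.642, pass) into 8/31 v 0/14 (0.383, fail).

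**Step 3: move away from the boundary.** The same relabelling of one rejecting patient takes 3/30 v 0/15 from 0.964 to 0.994 (2/29 v 1/16), and 12/30 v 0/15 from 0.034 to 0.120 (11/29 v 1/16). Neither decision changes.

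**Step 4: how often the trial lands where one relabelling matters** (assumed control rate 5% to 10%).

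| True CFZ533 rate | Rejecting patient moved: fail to pass | Non-rejecting patient moved: pass to fail |
|---|---|---|
| 10% | 0.6–1.1% | 0.7–0.8% |
| 20% | 9.3–12.2% | 7.3–9.3% |
| 25% | 13.8–15.6% | 8.7–12.1% |

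Each figure is the chance that the as-randomised counts fall where such a move would change the decision. A patient of that kind must also exist, and the documents give no expected number.

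**The case against.** The strongest objection concerns the remedy. The PoC rule asks whether CFZ533 is less than 20 points worse, so it is of non-inferiority type. Keeping a tacrolimus-treated patient who does not reject in the CFZ533 denominator lowers the CFZ533 rate and makes a pass easier. The third row of step 2 shows this: as randomised passes and as treated fails. This stands. It is a reason to report both analyses, not to omit the randomised one.

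A reader might infer that the current rule favours CFZ533. The documents do not support that, because the direction depends on whether the diverted patient rejects.

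A reader might also infer that the dose condition removes control patients who fail before their first tacrolimus dose. The glossary counts background therapy as study drug, and Protocol Section 5.5.4 starts MMF immediately after randomisation and no later than 24 hours after reperfusion, or by local practice. Few transplanted patients could fail the condition, so it is a minor point.

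Initial crossover would also be a protocol deviation, since Section 5.5.4 requires the assigned regimen to be followed from randomisation. SAP Section 6.1.4 notes that some patients switched regimen, but does not say that any began on the other arm's drug. Later switchers are handled by on-treatment counting and by censoring in the Poisson analysis. They should not be read as moved to control.

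Knowledge of the arm is also less clear than Section 5.4 suggests. Table 18-1 marks subject and treating physician as blinded at allocation and unblinded at treatment administration. The two places need to be reconciled. Neither settles which arm a patient should be counted in.

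**Conclusion.** The point holds as a gap in the plan. Both documents count patients by treatment received, and no tBPAR analysis by randomised arm is visible, so the PoC comparison is not protected by randomisation for any patient whose initial treatment differs from the assigned one. This rests on the visible text, since parts of Protocol Sections 9.4.1 and 9.4.2 are redacted.

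The effect on the decision is limited to counts at or next to the boundary. Given a diverted patient, one relabelling could change the decision in about 1% of trials at a true CFZ533 rate of 10%. At 20% the figure is about 7–12% for each type of move. A reader might infer from the examples that one patient is likely to decide this trial. That does not follow, because no allocation-stage crossover is documented. A yes/no rule at 45 patients is also fragile near its threshold under any analysis set: analysing as randomised removes this route to a changed decision, not the fragility.

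Counting only on-treatment events (Protocol Section 9.4.2) is a separate departure from the randomised comparison. It is not resolved by redefining the set.

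**What to change.** In Protocol Section 9.1 and SAP Section 4:

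- Name the FAS as the set for the primary tBPAR analysis.
- Define it as all randomised and transplanted patients, analysed in the randomised arm.
- Keep treatment received for the Safety, PK and PD sets. The PD set is built from the FAS, so its dose condition and treatment-received grouping should be written out separately.
- Report the PoC posterior probability by treatment received as a sensitivity analysis beside the primary result.
- List by randomised arm every patient who is excluded, including those not transplanted and replaced, or whose initial treatment differed from the assigned one.

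The change needs no new patients, visits or data, and the decision rule and planned numbers stay as they are. The cost is slightly more analysis. The drawback is that patients treated off their assigned arm may dilute the difference in the as-randomised result, which is why the second analysis belongs beside it. If every transplanted patient was dosed and started on the assigned arm, the two analyses coincide.
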